In the retrospective study carried out at the CHUS by our research team²⁸, the results of which have not yet been published, the NESIS group had complete resolution of TNS in 14% when treated with usual antiepileptics. Upon failure of usual treatments and after a change to recognized treatments for cortical depression (Topiramate and Lamotrigine), 100% of patients had resolution of symptoms. It is important to understand that the treatment of the patients in this study was administered entirely within the hospital, a poorer compliance is therefore to be expected for our patients who will continue their treatment at home, which could affect the power of our study. However, these proportions are still those which come closest to what could be found in our study.

Calculation of sample size from proportions :

$$2N(by group) = \frac{4(z\alpha + z\beta)^2 \bar{p}(1 - \bar{p})}{(pc - pexp)^2}$$
$$2N(by group) = \frac{4(1,960 + 1,282)^2 0,57(1 - 0,57)}{(0,14 - 1)^2}$$
$$2N = 14$$
$$N = 7$$

The size calculated with the core studies as well as with the proportions taken in the retrospective study in our center are similar (8 and 7, respectively). In order to prevent a lack of potency for the reasons mentioned above, a slightly larger size will be preferred, and 15 patients seems a reasonable number. This calculation represents the sample size that one should aim for in each group (intervention and active comparator) within the

NESIS subgroup. It will therefore be necessary to analyze the results of nearly 30 patients in the NESIS group.

As the non-NESIS patients are not part of our primary outcome and are less numerous than the NESIS (72% compared to 28%²⁸), they will be included in the study without a specific target, up to a maximum of 30 patients and their results will be analyzed descriptively.

[figure not shown]
α = 0,05 by convention β = 0,10 by convention
β = 0,10 by convention
p = Mean proportion between 2 groups
((0,14+1)/2 = 0,57)
pc = comparator's proportion (14% = 0,14)
<pre>pexp = intervention's proportion (100% = 1)</pre>
Z = normalized form of the error according
to constant values without units

Considering the dropout or loss rate at follow-up,

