As indicated in our research question, our study mainly aims to verify the effectiveness of TPM (dependent variable) compared to LEV in the NESIS group compared to the non-NESIS group (independent variable). For this, evaluations with standardized questionnaires will make it possible to assess the resolution of neurological symptoms (dichotomous variable). In addition, reductions in the frequency, intensity and duration of TNS will be assessed (continuous variables).

The tolerance of the two study drugs will also be compared. There will be a comparison of the number of failures in the two groups (dichotomous variable) and the percentage of patients with side effects (continuous variable).

Table 3 - Variables					
Variables	Measurement method	Measuring instrument			
Topiramate efficacy	Complete reduction of neurologicalMedical assessmentsymptoms (yes or no)a form				
	Average reduction in TNS frequency (nb/week)				
	Average reduction in TNS duration (minutes)				
Levetiracetam efficacy	Complete reduction of neurological symptoms (yes or no)	Medical assessment using a form			
	Average reduction in TNS frequency (nb/week)				
	Average reduction in TNS duration (minutes)				
Topiramate tolerance	Type of side effects (e.g. dysphasia, paraesthesia, fatigue, drowsiness, dizziness)	Medical assessment using a form			
	Severity of side effects (graded according to CTCAE terminology)				
	Number of dropouts (%)				
	Medication deemed useful by the patient (yes or no)				
Levetiracetam tolerance	Type of side effects (e.g. irritability, depression, drowsiness, headache, fatigue)	Medical assessment using a form			

Table 3 - Variables

	Severity of side effects (graded according to CTCAE terminology) Number of dropouts (%) Medication deemed useful by the patient (yes or no)		
Demographic data	See table 1 above	Standardized questionnaire completed by a member of the research team	
TNS characteristics	See table 2 above	Standardized questionnaire completed by a member of the research team	
Electrocorticogra phy	Two "strip" type ECoG electrodes, followed by 72-hour monitoring or until recording for 5 episodes of transient neurological symptoms.	Search for epileptiform activity or cortical depolarizations.	

Measuring instrument

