The intervention (Topiramate versus Levetiracetam) will be initiated in the hospital and then, initially, a prescription will be given to the patient for the community pharmacy.

Topiramate will be initiated at 50 mg BID, with an expected increase of 50 mg per week until symptoms are controlled or up to a maximum titration of 100 mg BID.

Levetiracetam will be initiated at 500 mg BID, with an expected increase of 1000 mg divided into 2 doses per week until symptoms are controlled or up to a maximum titration of 1500 mg BID.

The drugs could be reduced or stopped after discussion with a doctor because of side effects or no improvement in TNS.

Follow-up

There will be two phone follow-ups (2nd week and 6th month), as well as two clinical follow-ups (2nd and 4th month).

Phone follow-up: Medical evaluation by a resident, neurologist or neurosurgeon participating in the study. The person administering the assessment will follow a standardized questionnaire so as not to omit information relevant to the study. This assessment includes characterization of transient neurological symptoms and investigation of side effects.

Clinical follow-up: The patient will bring his study notebook to the appointment, in which he will have recorded the various TNS or side effects that have occurred in recent weeks. The appointment will be made by a neurologist or a neurosurgeon (all patients will have a meeting with each of the two specialists). The doctor will therefore carry out an evaluation of TNS and side effects, by completing the standardized questionnaire, which will help to limit the missing data.

The last follow-up will take place at 6 months, a date that we have based on the various studies in cortical depression which have demonstrated maximum effectiveness of TPM at 17 weeks²³. As we did experience in our community, we believe that a significant difference could emerge even earlier.

Losses during follow-up: patients who do not come to the follow-up appointment will be contacted again. In the event of a refusal to attend follow-up or a second absence from an appointment, with the patient's consent, a medical assessment may be completed by phone.

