If the patient wishes to stop the antiepileptic drug, a trial of smaller doses of the same treatment will be offered. Upon refusal, or failure despite a reduction in doses, TPM will be offered to the patient if he had LEV and vice versa. This change of group will only be possible after 2 months from the beginning of treatment. These data will not be included in the calculation of the primary outcome, but can still be analyzed as a secondary outcome to assess whether changing patients from one group to another allows them to fully resolve the TNS. Patients who fail both treatments, or who refuse to attempt the treatment in the other group will be excluded from the remainder of the study and treatment with another antiepileptic recognized in the treatment of focal seizures as well as an usual follow-up will be offered.

Participant calendar

Table 4 – Participant calendar

Recruitment (Day 1)	Randomizatio n (After recruitment)	Phone follow-up (Week 2)	Clinic follow-up (Month 2)	Clinic follow-up (Month 4)	Phone follow-up (Month 6)
Standardized questionnaires : Epidemiological	Start of treatment	Medical assessment with	Medical assessment with	Medical assessment with	Medical assessment with
data Clinical features	EEG daily x 2 MRI if needed	standardized questionnaire	standardized questionnaire	standardized questionnaire	standardized questionnaire

Collection method

Sources: Data will be collected initially with the help of the patient's medical record. Subsequently, the rest will be completed entirely by the patient or his family. The evaluations will be guided by standardized questionnaires.

For patients with ECoG, continuous waveforms will be recorded for the entire period the electrode will be implanted, either up to the recording of 5 TNS episodes or up to 72 hours of recording.

The data will be collected double blind. The person administering the questionnaire and the person analyzing the data will not know the patient's group. In addition, a study number will be assigned to all patients during randomization and this is going to identify the patients on the questionnaires. Thus, the data will be entered into the Excel software anonymously. Following the study, the data will be kept for a period of 25 years, in a file locked with a password that will be in the research nurse's locked filing cabinet.

Data analysis

Statistics

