Statistical analysis of the various data will be done with the help of the Statistical Package for the Social Sciences (SPSS) software. Most of the data will be analyzed by members of the research team. If necessary, the statistician of the CRC (Clinical Research Center) will be consulted.

The results will be analyzed by "intension-to-treat" given the expected dropouts in the two treatment groups.

Primary outcome: To assess the efficacy of TPM compared to LEV in the treatment of TNS in the context of SDH with negative EEG. To do this, it will be necessary to compare the rate of complete resolution of symptoms between the two groups. Our study comprising two independent groups and this variable being dichotomous (resolution: yes or no), a Chi-Square test will be used. This same test will also be used to compare the response of TPM in the NESIS versus non-NESIS subgroups and the same comparison with LEV will also

be performed. Subsequently, as sub-analyzes, the decrease in the frequency, intensity and duration of episodes (continuous variables) will also be compared in the two groups using a Student's T-test after validation of assumptions underlying the test.

Secondary outcome: tolerance to the antiepileptics used. To do this, we will analyze the comparison of the dropout rate (dichotomous variable: yes or no) and the side effect rate (categorical variable) using a chi-square test.

Degree of significance

We retained a significance level corresponding to an error α of 5%, whether a value p<0.05. The accepted beta error (β) is 10%, for a power of 90%.

Missing data

Patients with a large number of missing data or not including the data necessary to calculate the primary outcome will be excluded from the study. Those with some missing data that do not allow certain calculations of secondary outcomes will be kept in the study, however, the sample sizes of these analyzes will be clarified during writing.

Oversight mechanism

An independent results and dropout rate monitoring committee will not be necessary. However, monitoring will be carried out by the project team.

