Because TPM causes more side effects than LEV, compliance in this group may be lower. To limit the impact of this bias, active monitoring will be carried out with patients in the event of significant side effects, in order to reduce the dose of their treatment. This will limit drop-outs, as well as encourage better compliance. Then, the antiepileptics will be introduced gradually, in order to limit the side effects which would lead to a decrease in compliance.

Desirability bias

Because patients will know with which antiepileptic drug they will be assigned to, they could involuntarily change their different responses during assessments. Indeed, they might be tempted to demonstrate that TPM, treatment intervention, is more effective than it actually is. The same goes for side effects, which might be exaggerated by a patient knowing to take TPM, which is known to cause more side effects. To limit this bias, with the agreement of the ethics committee, we will approach patients during consent in a non-nominal manner. Indeed, while explaining that the two treatments are as effective as each other in epilepsy, we will explain that we want to demonstrate whether there is superiority of one of the two drugs over the other. Our hypothesis considering TPM being more efficient would remain confidential especially as this remains hypothetical. In the same sense, upon consent, all possible side effects will be presented in the form of a list, not distinguishing which are found more with which antiepileptic. Thus, even knowing the antiepileptic medication prescribed, patients will not be able to influence their responses for or against a particular treatment, not knowing which characteristics belong to which treatment. The two groups will therefore have the same potential information regarding their antiepileptic drug.

Other limitations :

The effect of Leveracetam on cortical depolarizations remains conflicting, however, if present, it may lessen the impact of our results. In addition, the favorable natural course of cortical depolarizations could mask the significant difference between our two groups.

Time and personnel management

Initial and follow-up in-clinic assessments will be performed during regular hospital hours. Telephone assessments will be carried out during the day or evening by a member of the research team.

Ethics

Consent

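### The dropout and failure measure of tolerance is not limited by cause, so stops for lack of effect can shrink or reverse the tolerance difference the protocol expects

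*Protocol*

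**What the plan says.** Tolerance is the secondary outcome in Data analysis, Statistics: "we will analyze the comparison of the dropout rate (dichotomous variable: yes or no"). The same sentence adds the side effect rate and names a chi-square test for both. The Variables section describes the comparison differently: "There will be a comparison of the number of failures in the two groups", together with the percentage of patients who have side effects. Table 3 lists, for each drug, the type of side effect, its CTCAE severity, the number of dropouts and whether the patient found the drug useful.

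Neither dropout nor failure is defined. Three other places bear on their meaning:

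- Intervention: "The drugs could be reduced or stopped after discussion with a doctor because of side effects or no improvement in TNS".
- Follow-up: a patient who wants to stop is offered a lower dose and then the other drug. Those who fail both, or decline the second, leave the study. On timing: "This change of group will only be possible after 2 months from the beginning of treatment".
- Oversight mechanism, safety monitoring: dropout and side effects that require discontinuation are two separate items.

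The expected direction of the true difference is given under Compliance bias: "Because TPM causes more side effects than LEV, compliance in this group may be lower". The follow-up form (Appendix 4) asks why treatment was discontinued, but no stated analysis uses the answer.

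**The concern.** A patient who stops because the drug did not help has had an efficacy failure, not an intolerance. If dropout or failure is counted without regard to cause, that patient still enters the tolerance comparison. The mixing would be harmless if such stops were equally common in both arms, but the protocol's planning assumptions say they will not be. In Sample size, "the NESIS group had complete resolution of TNS in 14% when treated with usual antiepileptics", against 100% after a change to TPM or lamotrigine.

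So the better TPM works, the worse LEV looks on this measure, whatever the side effects. A report could then credit TPM's efficacy twice, the second time as better retention presented as tolerance. That matters because the protocol expects TPM to cause more side effects, and a risk-benefit statement needs that cost shown cleanly.

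**Working it through.** **The plan's own figure.** The protocol gives no number for the tolerance comparison. The nearest figure that uses the same 14% and 100% is the sample size from proportions:

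2N = 4 × (1.960 + 1.282)² × 0.57 × 0.43 / 0.86² = 13.93, so 2N = 14 and N = 7 per arm. This reproduces.

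**Inputs from the protocol.** Resolution r in NESIS is 14% (used for LEV) and 100% (used for TPM). The target is 15 analysed per arm; 42 NESIS patients enrolled is 21 per arm. Total recruitment is 56, which leaves 56 − 42 = 14 non-NESIS. The Introduction reports 100% response to standard antiepileptics in non-NESIS patients. On the test level: "We retained a significance level corresponding to an error α of 5%, whether a value p<0.05".

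**Assumptions not in the protocol.** a = proportion stopping for side effects: either 5% LEV and 20% TPM, or 10% LEV and 30% TPM. q = share of the remaining non-responders who stop for lack of effect and are counted as dropouts or failures, from 0 to 1.

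**Formula.** Any-cause dropout = a + (1 − a)(1 − r)q. In NESIS:

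- TPM: r = 1, so dropout = a, whatever q is.
- LEV with a = 5%: 0.05 + 0.95 × 0.86 × q = 0.05 + 0.817q.
- LEV with a = 10%: 0.10 + 0.90 × 0.86 × q = 0.10 + 0.774q.

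| q | LEV (a = 5%) vs TPM 20% | LEV (a = 10%) vs TPM 30% |
|---|---|---|
| 0 | 5% vs 20% | 10% vs 30% |
| 0.25 | 25% vs 20% | 29% vs 30% |
| 0.50 | 46% vs 20% | 49% vs 30% |
| 0.75 | 66% vs 20% | 68% vs 30% |

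**Break-even q in NESIS.** 0.15 / 0.817 = 18% for 5% and 20%; 0.20 / 0.774 = 26% for 10% and 30%.

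**All patients.** If tolerance is compared in all 56 and non-NESIS patients have no stops for lack of effect, LEV non-response is 0.75 × 0.86 = 64.5%. Break-even becomes 0.15 / (0.95 × 0.645) = 24% and 0.20 / (0.90 × 0.645) = 34%. At q = 0.25 with 5% and 20%, dropout is 20.3% on LEV against 20% on TPM, which is effectively a tie.

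**Smaller efficacy gap.**

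- Resolution 80% vs 40%, a = 10% and 30%: 0.30 + 0.70 × 0.20q = 0.10 + 0.90 × 0.60q gives q = 0.20 / 0.40 = 50%.
- Resolution 70% vs 50%, same a: q = 0.20 / (0.45 − 0.21) = 83%.
- Resolution 70% vs 50%, TPM side-effect stops 40%: q = 0.30 / (0.45 − 0.18) = 1.11, so there is no reversal at any q.

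**Chance of a significant result.** Exact enumeration of the uncorrected chi-square test, NESIS, a = 10% and 30%, at 15 and 21 per arm. LEV significantly worse: 18% and 24% at q = 0.50; 55% and 70% at q = 0.75. If only side-effect stops are counted, TPM is significantly worse with probability 28% and 38%, and LEV with probability near zero, whatever q is.

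**The case against.** Five points can be made for the plan.

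1. Dropout is not the whole tolerance outcome. The sentence goes on to the side effect rate, and Table 3 adds type and CTCAE grade. Stops for lack of effect do not inflate these, so a report that follows the plan would still show TPM's side effects. This stands, and it confines the point to one component.
2. The protocol never says all-cause. Elsewhere it discusses dropouts mainly in connection with side effects, and an analysis plan not seen here could define the term. This stands in part: the meaning is open. But safety monitoring lists dropout apart from side effects that force discontinuation, which favours the broader sense, and the protocol itself assigns the unrestricted measure to tolerance.
3. Stopping a drug is not the same as leaving the study. A LEV non-responder may switch after two months and stay. This stands. High LEV dropout then needs refusals of the switch, early exits, or a switch being counted as a dropout or failure, and the protocol settles none of these.
4. The 14% and 100% are NESIS rates from a retrospective in-hospital series; the 100% is for TPM or lamotrigine after usual drugs had failed. This stands, and it is why the all-patient and smaller-gap results are shown.
5. A reader might infer that, under intention to treat, a TPM side effect in a LEV patient who switched would be charged to LEV. The protocol does not say so. It keeps post-switch data out of the primary outcome and allows a secondary analysis of them, and Table 3 sets out tolerance by drug. Attribution after a switch is simply unstated.

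**Conclusion.** The point holds for the dropout and failure component of tolerance. As written, that component is not limited by cause, and the protocol's planning rates put expected non-response almost wholly on LEV. It can therefore understate or reverse the difference expected under Compliance bias.

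In NESIS the reversal starts at q of about 18% (intolerance 5% and 20%) or 26% (10% and 30%). It starts at about 24% and 34% if all 56 patients are compared, and there may be none if the efficacy gap is small. Both intolerance rates and q are assumptions.

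A reader might go further and conclude that LEV will look poorly tolerated, or that the whole tolerance assessment misleads. The documents support neither: the first depends on undocumented rates, and the second ignores the side effect rate and the CTCAE grading. The measure should be changed, but it is one part of a secondary outcome and leaves the primary comparison untouched.

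**What to change.** In Variables and in Statistics, replace dropout rate and number of failures, as tolerance measures, with discontinuation of the allocated drug because of side effects. Then:

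- Take the cause from the reason already asked in Part 2 of the follow-up form. Check that the item also captures stops made together with a doctor; its wording is damaged in the copy reviewed, so its present scope is uncertain.
- Report stops for lack of effect as an efficacy result, and any-cause stopping as retention.
- State whether a switch to the other drug counts as a discontinuation.
- Count side effects on the allocated drug up to any switch, and tabulate later events separately by drug taken.

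The cost is wording in two sections and possibly one added option on the form, with no extra visits or patients. The downsides are fewer events in the tolerance comparison (28% to 38% chance of detecting 30% against 10% at 15 to 21 per arm) and reliance on the recorded reason. The result is better given as an estimate with its confidence interval than as a test alone.

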probably around 30-40%, a sample of a total of 42 patients with NESIS seems justified. Then, considering that nearly a third of patients will have a NESIS score of less than 4 (non NESIS), 56 patients should be included in the study. Finally, given the number of refusals to participate in the study, probably nearly half of the patients, we plan to approach at least 120 patients.

The final recruitment target is therefore 56 patients (Figure 2).

Figure 2 – Patients distribution

Sample disponibility

The number of participants to be randomized is acceptable and feasible but will require a multi-center design. In fact, during the retrospective study at the CHUS from March 2016 to March 2018²⁸, 18 patients with TNS in the context of cSDH with negative EEGs were identified. Thus, considering at least 4 centers participating in the study, the inclusion of 56 patients in 3 years seems realistic. Moreover, the NESIS entity being newly recognized (mentioned only since 2018), the incidence of NESIS is probably higher than what was found between 2016-2018, the patients being now more easily identified and classified.

Patient recruitment

Patients will initially be identified by neurosurgeons and neurologists from participating centers. These physicians will be aware of the existence of our study and will have the list of inclusion and exclusion criteria. They will therefore be able to inform us when a potential candidate is hospitalized.

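### The protocol promises intention-to-treat because dropouts are expected, then excludes randomised patients who lack primary-outcome data, so the primary test as written is a complete-case analysis

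*Protocol*

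**What the plan says.** - Data analysis, Statistics: results are analysed by intention-to-treat, and the reason given is "given the expected dropouts in the two treatment groups". The primary outcome is complete resolution of symptoms (yes or no), compared between arms by chi-square.
- Missing data: the exclusion has two triggers. The first is "Patients with a large number of missing data", with no threshold. The second covers patients "not including the data necessary to calculate the primary outcome will be excluded from the study". Patients who lack only secondary-outcome data are kept.
- Sample size: "It will therefore be necessary to analyze the results of nearly 30 patients in the NESIS group". The dropout or loss rate is "probably around 30-40%, a sample of a total of 42 patients with NESIS seems justified". The planning rates are 100% resolution on drugs active against cortical depression and "complete resolution of TNS in 14% when treated with usual antiepileptics".
- Intervention: "The drugs could be reduced or stopped after discussion with a doctor because of side effects or no improvement in TNS".
- Follow-up: after a refusal or a second missed visit, "a medical assessment may be completed by phone". Data after a change of drug do not count for the primary outcome. Patients who fail both drugs or decline the change are excluded from what remains of the study.
- Compliance bias and Risks of participating: compliance may be lower on TPM, and its side effects are expected to cause some loss to follow-up.
- Process, Initial meeting: a patient randomised before surgery starts the drug only if symptoms persist afterwards.

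**The concern.** Intention-to-treat is adopted in order to cope with dropouts, and the next rule removes the dropouts whose outcome is missing. Both sentences cannot be followed. Whoever runs the analysis must choose between them after randomisation, and the undefined amount of missing data leaves further exclusions to judgement.

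The choice matters because missing outcomes are unlikely to be random. The protocol ties stopping the drug to side effects and to lack of improvement, and expects side effects to cause loss on TPM. If lost patients are more often unresolved than those who stay, exclusion inflates the resolution rate. If this differs between arms, in amount or in reason, the TPM–LEV comparison is biased. Equal loss rates do not guarantee zero bias.

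**Working it through.** **Reproducing the plan's figure.** The target is 2 × 15 = 30 NESIS patients analysed. The stated 42 equals 30 × 1.40, and is close to 30/0.70 = 42.9. At 40% loss, keeping 30 would need 30/0.60 = 50. So 42 is an allowance for losses that leave the analysis.

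**Patients affected.** If every expected loss lacks the outcome, 42 × 0.70 = 29.4 and 42 × 0.60 = 25.2 are analysed. The two sentences then differ over 42 × 0.30 = 12.6 to 42 × 0.40 = 16.8 patients, about 13 to 17.

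**Bias under exclusion (illustration).** Let p be the true resolution rate, d the loss rate and f the share of lost patients who are unresolved. The rate among those analysed is (p − d(1 − f))/(1 − d). Assumed, because the protocol gives no loss rate by arm: 21 per arm, d = 0.40 (TPM) and 0.30 (LEV), and equal true rates, so every rejection is false. Rejection rates come from exact enumeration of resolved, unresolved and lost counts, with the uncorrected chi-square at two-sided 5%.

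- Pattern A: all lost patients unresolved in both arms (f = 1).
- Pattern B: TPM losses unrelated to symptoms (f = 1 − p), all LEV losses unresolved (f = 1). This is an extreme case.

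| True rate, both arms | A: TPM vs LEV as analysed | A: rejection | B: TPM vs LEV as analysed | B: rejection |
|---|---|---|---|---|
| 30% | 50% vs 43% | 7.2% | 30% vs 43% | 11.0% |
| 40% | 67% vs 57% | 8.4% | 40% vs 57% | 15.2% |
| 50% | 83% vs 71% | 10.8% | 50% vs 71% | 21.8% |

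Example, pattern A at 40%: 0.40/0.60 = 0.667 and 0.40/0.70 = 0.571. The false gap favours TPM in A (7–12 points) and LEV in B (13–21 points).

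Softer versions, with 80% of the affected losses unresolved:
- A gives gaps of 2–7 points and 5.7–7.1% rejection.
- B, with only 80% of LEV losses unresolved, gives gaps of 4–13 points and 6–11% rejection.

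Reference points: with equal 35% losses, all unresolved in both arms, rejection is 5.2–5.5%. With equal 35% losses in pattern B and a true 40%, it is 21.2%.

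**At the planning rates.** With all LEV losses unresolved, LEV reads 0.14/0.70 = 20% to 0.14/0.60 = 23%, against 100% on TPM. The conclusion would not reverse.

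**Missing counted as not resolved.** The analysed rate becomes p − d(1 − f), over all 21 per arm.

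| Situation (40%/30% loss) | Exclusion | Missing = not resolved |
|---|---|---|
| A, equal true 30–50%: false rejection | 7.2–10.8% | 4.6–5.6% |
| B, equal true 30–50%: false rejection | 11.0–21.8% | 15.4–26.1% |
| B, true 80% vs 40%: power | 25.0% | 7.8% |
| Losses unrelated in both arms, true 80% vs 40%: power | 59.1% | 27% |

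In pattern B at a true 40% this rule reads 0.40 × 0.60 = 24% vs 40%. With equal 35% losses it does better than exclusion there (17.1% against 21.2%). At 100% vs 14% with unrelated losses, rates become 60–70% vs 8–10% and power is about 96–99%.

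**The case against.** The conflict between the two sentences is hard to dispute. The case against concerns how much follows from it.

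- **The count.** A reader might infer that only 25 to 29 NESIS patients will be analysed. The protocol does not support that. Stopping the drug is not the same as lacking an outcome: the follow-up form records persistence of symptoms regardless, missed visits lead to re-contact and possibly a phone assessment, and the month-6 visit is itself a call. The figure is a worst case. This stands.
- **The direction.** A reader might infer that exclusion favours TPM, or the reverse. Neither is supported. The 14% is non-response to usual antiepileptics, not loss. Lack of improvement is linked to stopping the drug, not to missing data. A change of drug is allowed only after 2 months and a clinic visit falls at month 2, so a LEV non-responder may already have symptoms recorded. Pattern B is therefore a possibility, not a forecast.
- **The repair.** A reader might take intention-to-treat to require that missing counts as failure. The figures above do not support that as a general rule: it controls error in pattern A, but in pattern B with 40%/30% loss it has more false rejection and less power than exclusion.
- **Change of drug.** The Follow-up wording could be read as removing these patients from the analysis. It reads more naturally as prospective, so it is an ambiguity, not a second contradiction.

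A separate analysis plan might add detail, but the finding concerns a rule that the protocol states, not one that it leaves out.

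**Conclusion.** The point holds and should be fixed. The Missing data rule contradicts the intention-to-treat statement, and the sample size is planned on the exclusion. Confidence in the contradiction is high.

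The size of the harm is not known. It rests on how many outcomes are actually missing and how often those patients are unresolved in each arm, and the protocol gives neither. The 7–11% and 11–22% false-rejection figures are conditional on the assumed losses and true rates. The protocol's extreme planning rates are not threatened. The rule matters if the true difference is smaller, which is plausible because the Sample size section itself expects poorer compliance at home than in the inpatient series behind those rates.

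**What to change.** In Missing data, delete the exclusion for the primary outcome, including the undefined trigger. State instead that:

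- all randomised patients of the primary population are analysed in their assigned arm (the sample size is set on NESIS patients; the test description does not say so);
- every patient with a primary-outcome assessment is scored by it, whether or not the drug was stopped;
- one named rule, chosen in advance, applies when the outcome is missing;
- the complete-case result is reported, with a sensitivity analysis that varies the assumed outcome of missing patients separately by arm.

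In Follow-up, state that patients who change drug or leave remain in the denominator of their assigned arm. Say how randomised patients who never start the drug after surgery are counted.

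If missing is to count as not resolved, choose it knowing the trade-off above. The sensitivity analysis reveals its bias but does not correct the primary test.

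Cost: protocol wording and one sensitivity table, with no extra patients or visits. Reported rates and power may fall. For an assumed 70% vs 14% with 35% unrelated loss per arm, counting missing as not resolved gives 45.5% vs 9.1% and power 0.81, against 0.89 complete-case. With 40%/30% loss it gives 42% vs 9.8% and 0.71, against 0.88.
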